4. INTRODUCTION

4.1. Background

This study is being conducted as part of a series of studies for the clinical development of pegcetacoplan for advanced Age-related Macular Degeneration (AMD) (neovascular AMD and geographic atrophy [GA]). The trial will be conducted in compliance with this protocol, Good Clinical Practice (GCP), and applicable regulatory requirements. The subject population will comprise adult male and female subjects with GA secondary to AMD.

4.1.1. Age-Related Macular Degeneration

Age-related macular degeneration is the leading cause of severe vision loss in people over the age of 65 in the United States and other Western countries.² In the United States, about 1.75 million people have the advanced forms of AMD.³ The early signs of AMD (drusen and pigmentary changes) are common in individuals over age 65 and precede the late stage forms, which are visually devastating. The late stage forms of AMD are classified into either macular neovascularization (neovascular, wet, or exudative AMD) or GA.

Geographic Atrophy is a disease characterized by thinning and loss of the retinal pigment epithelium (RPE) and concurrent atrophy of photoreceptors and choriocapillaris. ^{4,5,6} Clinically, GA is characterized by gradually expanding atrophy leaving islands of dead retinal cells in the back of the eye. Although GA can result in significant visual function deficits in reading, night vision, and dark adaptation, and produce dense, irreversible scotomas in the visual field, the initial decline in visual acuity may be relatively limited if the fovea is spared. When the fovea is involved, GA quickly causes blindness.

Genetic susceptibility has become increasingly recognized as a risk factor and important contributor to AMD. More than 19 genetic polymorphisms have been demonstrated to influence AMD risk, with as many as 5 of these encoded by genes that modulate the complement system. Inflammatory processes, especially those mediated by complement are thought to play a key role in AMD.⁵ It is thought that these may contribute to loss of choriocapillaris, photoreceptors, and RPE cells.

GA is responsible for approximately 20% of all cases of legal blindness in North America (ie, BCVA 20/200 or worse) with increasing incidence and prevalence owing to a higher life expectancy.⁴ While there is treatment for exudative AMD with anti-VEGF therapies, no approved therapy exists for GA which is usually bilateral and relentlessly progressive. It represents a significant unmet need as it leads to significant visual impairment and affects more than 5 million people worldwide.¹³

An overview of available information regarding pegcetacoplan follows below. Further details can be found in the pegcetacoplan investigator's brochure (IB).²⁶

4.1.2. Pegcetacoplan

Pegcetacoplan is a PEGylated cyclic peptide inhibitor of complement C3. Pegcetacoplan is formed by 2 identical pentadecapeptides (combining a bioactive cyclic tridecapeptide C3-

inhibiting moiety and a 2-amino acid linker) covalently coupled to each end of a linear 40 kDa polyethylene glycol (PEG) chain. There are 2 peptide moieties per molecule of pegcetacoplan.

The peptide portion of the drug binds to complement C3 and is a broad inhibitor of the complement cascade, a biological process that is part of innate immunity and is involved in multiple inflammatory processes. The PEGylation of the molecule imparts slower clearance from the vitreous humor following administration.

Pegcetacoplan Intravitreal Injection 15 mg/0.1 mL will be provided as a 150 mg/ mL sterile solution of pegcetacoplan in stoppered glass vials. Pegcetacoplan is a sterile, isotonic solution in acetate-buffer, pH 5.0, containing trehalose. The drug product is packaged in 2R clear Type I glass vials with 13 mm FluroTec-coated chlorobutyl grey stoppers and sealed with 13 mm aluminum/polypropylene flip-off type seals.

[figure not shown]
4.1.3. Nonclinical Data

[figure not shown]
This section is intended to briefly summarize information on the safety, tolerability, and PK of intravitreal (IVT), intravenous (IV) and subcutaneous (SC) injections of pegcetacoplan. For complete and detailed information, refer to the IB.

As pegcetacoplan is only pharmacologically active in primates, the pivotal IVT toxicological studies have been conducted in cynomolgus monkeys. The safety and tolerability of IVT-administered pegcetacoplan has been assessed in a Good Laboratory Practice (GLP)-compliant pivotal chronic (9-month) repeat-dose study in cynomolgus monkeys. In addition, 2 GLP-compliant 2-month ocular bridging studies (the first comparing drug substance from 2 different CMOs, the second assessing the safety and tolerability profiles of 3 different formulations to support the Phase 3 clinical study) have been conducted in cynomolgus monkeys as well. Pegcetacoplan was observed to be minimally immunogenic in the 9-month study as evidenced by a lack of circulating antibodies in the majority of monkeys studied. The NOEL for chronic (9-month) IVT dosing was concluded to be >24.8 mg/eye. The results of this 9-month chronic study in cynomolgus monkeys support the safety of chronic IVT injections of pegcetacoplan at monthly or bimonthly intervals in humans.

PK assessments included in the chronic (9-month) study revealed serum concentrations of pegcetacoplan that were approximately dose-proportional 24 hours after the first IVT dose. The serum $t_{1/2}$ of IVT-administered pegcetacoplan, determined in a separate PK assessing a 10 mg/eye dose (in 50 μ L), was 10.4 days although the pegcetacoplan levels measured in the serum following infrequent IVT administration are orders of magnitude lower than pharmacological serum levels achieved with SC or IV administration.

Additional nonclinical studies in monkeys and rabbits, including assessments of other routes of administration (SC and IV), have further defined pegcetacoplan's safety profile. Pegcetacoplan has been shown to be generally tolerated through all 3 routes of administration assessed (IVT, SC, and IV), with no adverse effects observed in safety pharmacology studies (*in vivo* cardiopulmonary telemetry and *in vitro* hERG inhibition assay) and genotoxicity studies (Ames, *in vitro* aneugenicity and clastogenicity in TK6 cells, and *in vivo* clastogenicity in mouse micronuclei).

4.1.4. Clinical Data

The initial safety and tolerability of pegcetacoplan following IVT administration in humans was tested in an open-label, single dose escalation, Phase I clinical study in patients with wet age-related macular degeneration under protocol POT-CP043014 (NCT02461771). The study was conducted in multiple ophthalmology clinical sites in the US and Australia. A single dose of pegcetacoplan was administered on Day 1 to patients suffering from wet AMD currently receiving anti-VEGF standard of care. Three escalating doses of pegcetacoplan administered IVT were studied. Three subjects received 4 mg; 3 subjects received 10 mg, and 7 subjects received 20 mg. No serious adverse events (SAEs) or drug-related adverse events (AEs) of concern were observed. It was concluded that administration of a single dose of pegcetacoplan IVT up to 20 mg is safe and well tolerated.

A Phase 2 study (Protocol POT-CP121614; NCT02503332) to assess the safety, tolerability, and evidence of activity of multiple intravitreal injections of pegcetacoplan in subjects with geographic atrophy secondary to AMD has been completed. The study was conducted at multiple ophthalmology clinical sites in the US, Australia, and New Zealand. Subjects were randomized in a 2:1:2:1 manner to either receive pegcetacoplan IVT 15 mg monthly for 12 months; sham IVT monthly for 12 months; pegcetacoplan IVT 15 mg every other month for 12 months; or sham IVT every other month for 12 months.

This study demonstrated a statistically significant slowing of disease progression at Month 12 at the prespecified alpha of 0.1. Pegcetacoplan administered monthly showed a 29% (P=.008) reduction in the rate of GA lesion growth compared to sham and pegcetacoplan administered every other month showed a 20% (P=.067) reduction. Pegcetacoplan has been generally well tolerated. The most frequently reported AEs have been related to the injection procedure (intravitreal injection), which are commonly found in this type of study. An imbalance in new active choroidal neovascularization (CNV) in subjects treated with pegcetacoplan was observed and the risk of developing new exudation may be increased in subjects with a prior history of neovascular AMD in the fellow eye. One subject in the sham arm, 1/81 (1%) was observed to have developed new active study eye exudation compared with 25/165 (15%) subjects that received pegcetacoplan IVT injections, 26 subjects in total. Of the 25 pegcetacoplan treated subjects with new active CNV, 18 subjects received PM treatment and 7 subjects received PEOM treatment.

Seventeen of the 25 (68%) subjects that developed new active study eye CNV had a prior history of neovascular AMD in the nonstudy fellow eye. No significant imbalance in history of neovascular AMD in the fellow eye was observed among the 3 arms to explain the imbalance in new exudation observed in study eyes. Visual acuity data did not demonstrate clear differences between subjects developing new study eye exudation compared with those that did not.

A Phase 1b study (Protocol APL2-103; NCT 03777332) to assess the safety of pegcetacoplan in subjects with GA secondary to AMD and low vision is currently ongoing. This study is being conducted at multiple ophthalmology clinical sites across the US. Subjects receive monthly treatment with intravitreal pegcetacoplan for 24 months.

4.1.5. Rationale

4.1.5.1. Rationale for Pegcetacoplan for Treatment of Geographic Atrophy

The rationale for the use of a complement inhibitor in patients with AMD is based on evidence from both human and animal studies. Human biochemical, genetic, and clinical lines of evidence indicate that the complement system plays a role in the etiology of AMD. Complement components including C3, the membrane attack complex, and complement factor H, are present in drusen and basal laminar deposits in eyes from patients with AMD.^{7,8,9,10} Genetic variants of complement factor H, ^{8,11,12,13,14} C3, ^{15,16} complement factor I¹⁷ and other complement components of both the neovascular and atrophic forms of AMD. Patients with AMD also have signs of systemic complement activation, exhibiting higher serum levels of Complement Factor B, C3a, C5a, SC5b-9 (soluble terminal complement complex), C3d, and Ba compared to age-matched controls. ^{21,22,23,24}

4.1.6. Dose Selection

A single dose of 15 mg/0.1 mL injection administered monthly or EOM for 24 months will be tested in this study (see Section 7.3.1). Pegcetacoplan was well tolerated in a panel of animal toxicology studies. A 9-month, repeat-dose GLP study in cynomolgus monkeys was conducted to evaluate the safety of IVT injections of pegcetacoplan at doses up to 24.8 mg/eye at a frequency of 1 injection every 4 weeks.

In this pivotal chronic toxicological study conducted in monkeys, the NOEL was established as >24.8 mg of pegcetacoplan delivered intravitreally every 4 weeks for 9 months using a 100 μL injection. The volume of the human vitreous is approximately 4 mL, which is approximately 2.7-fold larger than the mean vitreous volume of cynomolgus monkeys, 1.5 mL.²⁵ Based on the difference in vitreous volume between man and cynomolgus and the NOEL defined in nonhuman primates, the human equivalent dose was determined to be 67 mg/eye every 4 weeks. The dose (15 mg/injection) of pegcetacoplan that will be evaluated in this clinical study is expected to result in drug concentrations approximately 4.5-fold lower that the NOEL observed in cynomolgus monkeys.

To support appropriate assessments of dose response to pegcetacoplan, pegcetacoplan is administered in 2 different frequencies in the study: monthly and every other month.

Physician feedback injecting a 200 mg/mL solution in the Phase 1 (Study POT-CP043014; NCT02461771) trial confirmed that 150 mg/mL is the highest practical concentration that can be routinely administered, which set the dose of the Phase 2 trial to 15 mg (ie, 0.1 mL of a 150 mg/mL solution). The 15-mg dose given monthly was found to be the most efficacious in the Phase 2 trial. The 15 mg dose given every other month demonstrated slightly less efficacy but offers a reduced treatment burden for patients and physicians.

4.2. Risk/Benefit

The Phase 1 (Study POT-CP043014; NCT02461771) and Phase 2 (Study POT-CP121614; NCT02503332) studies provide supporting evidence of a positive benefit-risk profile for the use of pegcetacoplan in treating patients with AMD, specifically patients with GA. These

preliminary results of an up to 28% reduction of GA progression rate support the evaluation of pegcetacoplan in a Phase 3 study.

The reported safety data from these studies demonstrated an acceptable safety and tolerability profile with no clinically significant safety concerns observed. A total of 178 patients have received at least 1 dose (15 mg/injection) of pegcetacoplan as part of these studies. In the Phase 2 study in patients with GA an imbalance in new exudation in subjects treated with pegcetacoplan was observed. Section 4.1.4 provides a summary of the study design and key results from both studies.

The safety monitoring practices employed by this protocol (complete ophthalmologic exam, IOP monitoring, OCT, fluorescein angiography, vital signs, hematology, serum chemistry, urinalysis, physical exam, vital signs, and AE questioning) are adequate to protect the subjects' safety. There are also risks associated with the ophthalmic procedures required for participants in this study. However, these are all standard procedures that are widely performed in ophthalmology.

In the days following any IVT injection, patients are at risk of developing sterile or infectious intraocular inflammation (eg, endophthalmitis). In recent studies conducted with pegcetacoplan IVT from a single manufacturer, events of transient moderate and severe intraocular inflammation have been observed. Other risks of IVT injection include traumatic cataract, retinal detachment, increased IOP, and hemorrhage.

The amount of blood (See Section 9.16) planned for collection from each subject over the 24 months of the study does not pose an undue risk in this patient population.

There is a potential health benefit for trial participants from receipt of study drug. If efficacious, pegcetacoplan is expected to alter the course of GA and slow its rate of progression.

5. STUDY OBJECTIVES

5.1.1. Primary Objective

To evaluate the efficacy of pegcetacoplan compared to sham injection in patients with GA secondary to AMD assessed by change in the total area of GA lesions from baseline as measured by fundus autofluorescence (FAF).

5.1.2. Key Secondary Objectives

To evaluate the efficacy of pegcetacoplan compared to sham injection in patients with GA secondary to AMD with respect to:

- Monocular maximum reading speed (study eye), as assessed by Minnesota Low-Vision Reading Test (MNREAD) or Radner Reading Charts (in select countries)
- Functional Reading Independence (FRI) index score
- Normal luminance best corrected visual acuity score (NL-BCVA) in the study eye

5.1.3. Secondary Objectives

- To evaluate the efficacy of pegcetacoplan compared to sham injection in patients with GA secondary to AMD with respect to:
 - Low luminance best corrected visual acuity score (LL-BCVA) in the study eye
 - o Low luminance deficit (LLD) in the study eye
 - o Total area of GA lesion(s) in the study eye
 - Monocular critical print size (study eye), as assessed by MNREAD or Radner Reading Charts (in select countries)
 - National Eye Institute Visual Functioning Questionnaire 25-Item Version (NEI VFQ-25) distance activity subscale score (in select countries)
 - o Macular functional response as assessed by mesopic microperimetry

5.1.4. Safety Objectives

- To evaluate the safety and tolerability of pegcetacoplan compared to sham injection in patients with GA secondary to AMD as indicated by:
 - Incidence and severity of ocular and systemic treatment-emergent adverse events
 - o Incidence of anti-therapeutic antibodies directed against pegcetacoplan
 - o Incidence of new active CNV in the study eye

5.1.5. Exploratory Objectives

- To evaluate the efficacy of pegcetacoplan compared to sham injection in patients with GA secondary to AMD as indicated by:
 - NEI VFQ-25 composite score
 - o NEI VFQ-25 near activity subscale score (in select countries)
 - o Comparison between study eye and fellow eye in change in GA lesion size
 - To evaluate the binocular maximum reading speed as assessed by MNREAD or Radner Reading Charts (in select countries)
 - To evaluate the binocular critical print size as assessed by MNREAD or Radner Reading Charts (in select countries)
- To evaluate the relationship between genetic polymorphisms associated with AMD with GA progression and response to pegcetacoplan
- To evaluate the incidence of new onset of subclinical CNV in the study eye
- To assess sensitivity and specificity of a digital reading speed application to detect disease progression / regression (optional, select sites)
- To assess sensitivity and specificity of a digital visual function application to detect disease progression / regression (optional, select sites)

6. PATIENT POPULATION

The study population includes approximately 600 subjects to be randomized at approximately 100 multinational sites. To participate in the study, subjects must be diagnosed with GA of the macula secondary to AMD in the study eye.

6.1.1. Inclusion Criteria

The study eye must meet all inclusion criteria. If both eyes meet the inclusion criteria, the eye with the worst normal luminance visual acuity at the screening visit will be designated as the study eye. If both eyes have the same visual acuity, the right eye will be selected as the study eye.

Ocular-specific inclusion criteria apply to the **study eye** only, unless otherwise specified.

- 1. Age \geq 60 years.
- 2. Normal Luminance best corrected visual acuity of 24 letters or better using Early Treatment Diabetic Retinopathy Study (ETDRS) charts (approximately 20/320 Snellen equivalent).
- 3. Clinical diagnosis of GA of the macula secondary to AMD as determined by the investigator and confirmed by the reading center.
- 4. The GA lesion must meet the following criteria as determined by the central reading center's assessment of FAF imaging at screening:
 - a. Total GA area must be ≥ 2.5 and ≤ 17.5 mm2 (1 and 7 disk areas [DA] respectively).
 - b. If GA is multifocal, at least 1 focal lesion must be \geq 1.25 mm2 (0.5 DA), with the overall aggregate area of GA as specified above in 4a.
 - c. The entire GA lesion must be completely visualized on the macula centered image and must be able to be imaged in its entirety and not contiguous with any areas of peripapillary atrophy.
 - d. Presence of any pattern of hyperautofluorescence in the junctional zone of GA. Absence of hyperautofluorescence (ie, pattern = none) is exclusionary.¹
- 5. Adequate clarity of ocular media, adequate pupillary dilation, and fixation to permit the collection of good quality images as determined by the investigator.
- 6. Meets the following criteria related to microperimetry:
 - a. Able to detect fixation target.
 - b. Total elapsed time to complete the 10-2 68-point exam is ≤ 30 minutes in duration.
 - c. Fixation losses must be $\leq 20\%$.
 - d. Subject is willing and able to undertake microperimetry assessment in the opinion of the investigator.
- 7. Female subjects must be:
 - a. Women of non-childbearing potential (WONCBP), or
 - b. Women of childbearing potential (WOCBP) with a negative serum pregnancy test at screening and must agree to use protocol defined methods of contraception for the duration of the study and refrain from breastfeeding for the duration of the study.

- 8. Males with female partners of childbearing potential must agree to use protocol defined methods of contraception and agree to refrain from donating sperm for the duration of the study.
- 9. Willing and able to give informed consent and to comply with the study procedures and assessments.

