Abbreviations: BCVA=best corrected visual acuity; CNV=choroidal neovascularization; DCFP=digital color fundus photography; eCRF=electronic case report form; FAF=fundus autofluorescence; FFA=fundus fluorescein angiography; FRI=Functional Reading Independence index; IOP=intraocular pressure; LL BCVA= low luminance best corrected visual acuity; MNREAD=Minnesota Low-Vision Reading Test; NEI VFG-25=National Eye Institute Visual Functioning Questionnaire 25-item Version; NIR=near infrared reflectance; OCT-A=optical coherence tomography angiography; SD-OCT=spectral domain optical coherence tomography; SE=study eye; Term=termination; VEGF=vascular endothelial growth factor.

Note: All ocular assessments are to be performed for both eyes unless annotated with 'SE' (study eye) in the above schedule. All assessments should be performed on the same day. All study visits should be scheduled and projected based on the Day 1 visit date.

- A. For subjects that discontinue the study early, the early termination assessments should be performed after a minimum of 30 days have passed from the last dosing visit. If a subject reports for a scheduled visit and decides to terminate early prior to dosing, then the visit should be considered the early termination visit and all early termination procedures should be performed. At Month 24, all subjects should be offered entry into an open-label study.
- B. At Day 1 (Visit 2), confirm subject eligibility through reviewing the inclusion/ exculsion criteria and receive confirmation of eligibility from the reading center.
- C. Significant medical/ surgical history from the previous 5 years. Anti-VEGF treatments (fellow eye) and invasive ocular procedures performed within the past 5 years and while on study should also be recorded. Any history of tobacco use should be recorded.
- D. Obtain prior to fluorescein angiography and before study drug administration.
- E. At screening, serum pregnancy should be performed for women of childbearing potential. If positive, subject is not eligible to continue in the study.
- F. Beginning at Day 1, perform the urine pregnancy test for women of childbearing potential at each treatment visit. If positive, perform a serum pregnancy test. If serum test is positive, study drug should not be administered and an early term visit should be completed.

APL2-304 Protocol Amendment 5 12 August 2020

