### **2.2.2. Key Secondary Endpoints**

The key secondary endpoints include:

- Change from baseline in the mean threshold sensitivity of all points (study eye) assessed by mesopic microperimetry at Month 24.
- Change from baseline in monocular maximum reading speed (study eye), at Month 24 as assessed by MNRead or Radner reading charts (in select countries).
- Change from baseline in mean FRI Index score (subject-level assessment) at Month 24
- Change from baseline in NL-BCVA score (study eye) at Month 24 as assessed by Early Treatment Diabetic Retinopathy Study (ETDRS) chart.

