## 5.2. Demographic and Other Baseline Characteristics

Demographic and baseline characteristics will be tabulated using descriptive statistics by treatment group and overall. Tables will be produced for the following analysis sets: ITT, Safety, mITT, Month 12 PP and Month 24 PP (as appropriate), and Genotyping. The following variables will be included in the tables:

The demographic data are:

- Age at screening (years) and in categories
  - < 65
  - 65-<75
  - 75-<85
  - $\geq 85$
- Sex
- Race
- Ethnicity
- Geographic Region (United States vs. Rest of World)
- Country
- Weight (kg) at baseline
- Height (cm) at baseline
- Body Mass Index ( $\text{kg}/\text{m}^2$ )
- Tobacco use status (ever, never)

Baseline characteristics will be summarized for both study eye and fellow eye whenever applicable. Baseline characteristics include:

- Study eye laterality (OD, OS)
- Study eye status (better-seeing eye vs. worse-seeing eye, based on NL-BCVA – in the case of ties, study eye status will be classified as the better-seeing eye)
- GA lesion size ( $\text{mm}^2$ ) (assessed by FAF)
- GA lesion size in categories, determined by reading center (as randomized status and actual status):
  - <  $7.5 \text{ mm}^2$
  - $\geq 7.5 \text{ mm}^2$
- GA lesion size categories (approximately tertiles based on APL2-303/304 combined data\*) – study eye only
- Square root GA lesion size (mm)

- GA lesion location (subfoveal involvement vs. non-subfoveal involvement) (assessed by FAF)
- GA focality (unifocal vs. multifocal) (assessed by FAF)
- Number of areas of atrophy (none, 1, 2-5, 6-10, 11-20, >20, cannot be determined) (assessed from FAF)
- Presence of double-layer sign (DLS) (assessed by SD-OCT)
- Central subfield thickness (CST) (assessed by SD-OCT)
- Presence of macular neovascularization (MNV) (i.e., subclinical CNV) (assessed by Optical Coherence Tomography Angiography (OCT-A))
- Presence of pseudodrusen (assessed by near-infrared reflectance imaging)
- Number of intermediate/large drusen (0-5, 6-10, 11-20, and >20) (assessed by color fundus photography)
- NL-BCVA in ETDRS letters
- NL-BCVA categories ( $\geq 70$ ,  $\geq 60 - < 70$ ,  $\geq 35 - < 60$ ,  $< 35$  ETDRS letters)
- NL-BCVA ( $< 60$  vs.  $\geq 60$  ETDRS letters)
- LL-BCVA in ETDRS letters
- LL-BCVA categories (approximately tertiles based on APL2-303/304 combined data\*) – study eye only
- IOP
- LLD in ETDRS letters
- LLD categories ( $< 20$  vs.  $\geq 20$  ETDRS letters)

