### **6.3.2.3. Mean FRI Index Score**

The mean FRI Index score will be calculated per the scoring algorithm in the FRI Index user's manual.

The mean FRI Index score will be summarized and analyzed in a similar fashion as the primary efficacy endpoint using MMRM described in Section 6.2.2. The model will include treatment (PM, PEOM, Sham), presence of CNV in the fellow eye (yes or no), and baseline GA lesion area ( $< 7.5$  mm^2 or  $\geq 7.5$  mm^2) as fixed effects; baseline mean FRI Index score and baseline study eye status (Better-seeing Eye vs. Worse-seeing Eye) as covariates, time (in months) as a factor; the time  $\times$  treatment interaction term as well as the baseline mean FRI Index score  $\times$  time interaction term.

The observed values for the mean FRI Index score will be summarized by treatment group and visit. Summaries will present the descriptive statistics for baseline, absolute values and change from baseline data.

The mean change from baseline in the mean FRI Index score  $\pm$  the standard error as well as the LS mean of the change from baseline in the mean FRI Index score  $\pm$  the standard error will be plotted over time by treatment group.

In addition, the mean FRI Index score will be converted to the FRI Level variable, as per the user manual, ranging from 1 (Unable to do) to 4 (Totally independent). The categorical changes from baseline (improvements (an increase in FRI level), minimal/no change (no change in FRI level), and worsening (decrease in FRI level)) will be summarized by treatment group and visit.

The shift from baseline in the FRI level over time will be presented by treatment group.

All FRI data will be listed for the ITT set.

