#### **6.3.2.4. NL-BCVA Score**

The mean NL-BCVA score for the study eye will be summarized and analyzed in a similar fashion as the primary efficacy endpoint using MMRM described in Section 6.2.2. The model will include treatment (PM, PEOM, Sham), presence of CNV in the fellow eye (yes or no), and baseline GA lesion area ( $< 7.5 \text{ mm}^2$  or  $\geq 7.5 \text{ mm}^2$ ) as fixed effects; baseline NL-BCVA score as a covariate, time (in months) as a factor; the time  $\times$  treatment interaction term as well as the baseline NL-BCVA score  $\times$  time interaction term. Note, for the second year, only timepoints that were measured for all three treatment groups will be included in the model.

The observed values for the NL-BCVA will be summarized by treatment group and visit for both the study and the fellow eye. Summaries will present the descriptive statistics for baseline, absolute values and change from baseline data.

The mean change from baseline in the NL-BCVA score for the study eye  $\pm$  the standard error as well as the LS mean of the change from baseline in the NL-BCVA score for the study eye  $\pm$  the standard error will be plotted over time by treatment group.

In addition, the categorical changes (improvements of  $\geq 15$ ,  $\geq 10$  to  $< 15$ ,  $\geq 5$  to  $< 10$ , and minimal/no change ( $-4$  to  $4$ ), worsening of  $\geq 5$  to  $< 10$ , and  $\geq 10$  to  $< 15$  and  $\geq 15$ ) for the study eye will be summarized by treatment group and visit.

The shift from baseline in the NL-BCVA of the study eye categories ( $\geq 70$ ,  $\geq 60 - < 70$ ,  $\geq 35 - < 60$ ,  $\geq 20 - < 35$ ,  $< 20$  ETDRS letters over time will be presented by treatment group and visit.

The above-mentioned ETDRS letter thresholds are based on WHO definitions for vision impairment and blindness. WHO criteria were implemented in an attempt to capture the progressive nature of Geographic Atrophy and the ultimate treatment goal of avoiding successive vision impairment and blindness through application of active treatment (Pegcetacoplan vs. Sham).

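### The FRI and VFQ-25 distance models code the two eyes' relative acuity only as a better/worse flag, although both baseline letter scores are collected; the cost is some precision, not bias

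*Protocol*

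**What the plan says.** **Eye selection.** Protocol 6.1.1 states that "the eye with the worst normal luminance visual acuity at the screening visit will be designated as the study eye". The rule applies only if both eyes meet the inclusion criteria, and equal acuity sends the choice to the right eye. If one eye qualifies, that eye is studied whether it sees better or worse.

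**Endpoint.** SAP 2.2.2 lists "Change from baseline in mean FRI Index score (subject-level assessment) at Month 24" as key secondary. SAP 6.3.1 tests it under alpha control (H3a, H3b) on pooled APL2-303 and APL2-304 data, or in APL2-304 alone under the fallback sequence of Figure 3. SAP 3.4 says that power was not calculated for the key secondary functional endpoints.

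**Model.** SAP 6.3.2.3 takes "baseline mean FRI Index score and baseline study eye status (Better-seeing Eye vs. Worse-seeing Eye) as covariates". The other terms are treatment, fellow-eye CNV (yes/no), baseline GA area category, month, month by treatment, and month by baseline FRI. SAP 6.4.4 uses the same structure, with the same flag, for the VFQ-25 distance score. SAP 5.2 bases the flag on NL-BCVA and adds that "in the case of ties, study eye status will be classified as the better-seeing eye".

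**Data available.** The visit schedules (Protocol Appendices A and C) place BCVA at screening and Day 1 with no study-eye mark, and their general note reads: "All ocular assessments are to be performed for both eyes unless annotated with 'SE' (study eye) in the above schedule". SAP 5.2 includes NL-BCVA letters among the characteristics tabulated for each eye: "Baseline characteristics will be summarized for both study eye and fellow eye whenever applicable". SAP 6.3.2.4 also reports NL-BCVA for both eyes at every visit.

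**The concern.** FRI asks how independently a person reads, so it can depend on either eye. The SAP accepts that relative acuity matters, since it adds study eye status to the models for its two subject-level MMRM endpoints. It then reduces that information to two levels. A fellow eye one letter better and a fellow eye forty letters better receive the same value. Equal eyes are coded as if the study eye saw better. The flag also uses baseline acuity (the last value on or before first dose, SAP 13.2), whereas the eye was chosen on screening acuity, so near-equal eyes can change class between the two.

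At stake is precision. Any FRI change that the eyes' letter scores could predict, beyond what the existing terms predict, stays in the residual. For an endpoint tested without a power calculation, covariate choice is one of the few means of improving precision still open at the analysis stage. The VFQ-25 distance score is not formally tested (SAP 6.5), so there the effect is only on the width of intervals.

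**Working it through.** **No figure to reproduce.** The documents give no standard deviation, effect size or power for FRI. The only power table (SAP Table 1) concerns lesion growth and has no bearing here. What follows is an assumed range.

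**Step 1: what the model knows of the fellow eye.** Three terms in SAP 6.3.2.3 speak to it: the flag (direction of the acuity difference), CNV yes/no (disease, not acuity), and baseline FRI (indirectly, through whole-person reading). No term holds either eye's letter score.

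**Step 2: how much of the fellow eye's letter score the flag carries.** Call this share q. The two acuities were simulated as jointly normal with equal spread, between-eye correlation r, and fellow-eye mean shifted by a number of SDs. All of these are assumptions.

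| r | shift (SD) | study eye worse | q |
|---|---|---|---|
| 0.2 | −0.5 | 35% | 0.241 |
| 0.2 | 0 | 50% | 0.254 |
| 0.2 | 0.5 | 65% | 0.240 |
| 0.2 | 1.0 | 79% | 0.202 |
| 0.5 | −0.5 | 31% | 0.145 |
| 0.5 | 0 | 50% | 0.158 |
| 0.5 | 0.5 | 69% | 0.145 |
| 0.5 | 1.0 | 84% | 0.108 |

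The values q = 0.10 and q = 0.25 are carried forward.

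**Step 3: precision.** Let ρ be the partial correlation between fellow-eye baseline letters and FRI change, given the other covariates. Then

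- residual variance with letters ÷ residual variance with flag = (1 − ρ²)/(1 − qρ²)
- fall in standard error = 1 − √ratio
- new power of a test that had 80% at two-sided 0.05 = Φ[(1.960 + 0.842)/√ratio − 1.960]

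Example, ρ = 0.3 and q = 0.10: ratio = 0.91/0.991 = 0.918, √ratio = 0.958, fall = 4.2%.

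| ρ | ratio (q = 0.25; 0.10) | fall in SE | 80% power becomes |
|---|---|---|---|
| 0.1 | 0.9925; 0.9910 | 0.4–0.5% | 80.3% |
| 0.2 | 0.9697; 0.9639 | 1.5–1.8% | 81.2–81.4% |
| 0.3 | 0.9309; 0.9183 | 3.5–4.2% | 82.7–83.2% |
| 0.4 | 0.8750; 0.8537 | 6.5–7.6% | 85.0–85.8% |

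**Step 4: sensitivity.** If the flag carried half of the information (q = 0.5), the ratio at ρ = 0.4 would be 0.84/0.92 = 0.913 and the fall 4.4%; at ρ = 0.1 it would be 0.99/0.995 = 0.995 and 0.25%. If ρ = 0, nothing is gained.

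The calculation covers the fellow-eye score in place of the flag; it credits nothing to the study-eye score. It also treats the covariate as fully effective at Month 24.

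**The case against.** The strongest case against is that this is a preference between two prespecified covariate sets, with a small gain of unknown size. Several parts of it stand.

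- A reader might infer that the model knows the fellow eye only through the flag. It does not: CNV status is a fixed effect, and baseline FRI reflects function with both eyes. Only the claim about acuity holds.
- A reader might infer that the study eye is nearly always the worse one, so that the flag is lopsided and almost empty. The worse-eye rule applies only when both eyes qualify. The exclusion for CNV history applies to the study eye only (Protocol 6.1.2), and patients with fellow-eye CNV are enrolled and stratified on it. In patients with one eligible eye, that eye may see better. No document gives the split.
- The usual result for cutting a normal variable in two (64% of explained variance kept at 50:50, 49% at 80:20) should not be applied directly. Among patients with two eligible eyes the rule makes the screening difference one-sided, so it is not normal. The same caution applies to the normal model in Step 2, which is why q was varied.
- A linear term for each eye is not the acuity of the better eye. It does carry the size and direction of the gap, which the flag cannot.
- The SAP already plans FRI subgroups by study eye status and by study-eye NL-BCVA (SAP 6.3.5, 6.2.5).
- Timing and scope matter. Sponsor analysts are unmasked at Month 12 (SAP 3.5), when key secondary endpoints receive nominal p-values (SAP 6.3). The formal test uses pooled data, so APL2-303 is involved, and its SAP is not available here.

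None of this explains why a collected, continuous baseline value should enter only in two-level form when the SAP itself treats it as relevant.

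**Conclusion.** The point holds as a modest improvement to the analysis. In SAP 6.3.2.3 and 6.4.4 relative acuity enters only as a two-level flag, and neither eye's baseline letter score is used although both exist.

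Two stronger readings might be inferred, and the documents support neither. The first is that the omission biases or conceals the treatment effect. Treatment is randomised, so leaving out a baseline covariate does not bias the contrast; it leaves the standard error somewhat larger than it need be. The second is that better adjustment would recover an effect weakened because the fellow eye does the reading. That would be a smaller true effect on a whole-person endpoint, and no covariate restores it.

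The gain is a fall of about 0.4% to 7.6% in the standard error. It rests on assumed partial correlations of 0.1 to 0.4 and on a flag carrying 10% to 25% of the variance in fellow-eye letters. The documents supply neither figure, and the upper end needs the letters to explain 16% (0.4²) of the remaining variance in FRI change.

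**What to change.** If the Month 12 unmasking has not occurred, add baseline NL-BCVA letter scores of the study eye and of the fellow eye as continuous covariates in SAP 6.3.2.3 and 6.4.4. Make the same change in the pooled APL2-303/304 FRI model, so that H3a and H3b use one covariate set. Keep the flag for the FRI subgroup analysis in SAP 6.3.5, and state whether it also remains a main-model term.

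If unmasking has occurred, leave the main model as it is, because changing it then would invite the charge of a data-driven choice. Instead, prespecify in SAP 6.3.3 a supportive FRI analysis that adds the two letter scores.

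The cost is a few words of SAP text and code, two degrees of freedom, and agreement with the APL2-303 plan. No new data are needed.
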